Dupclay et al 2012	Single dose blister packaging	63% (26%)	76 (25%)	Hypertension

Statistical Analysis

Mean medication adherence was calculated as the proportion of days covered (PDC) for hypoglycemic medications. The change in medication adherence (pre-intervention PDC subtracted from the post-intervention PDC = change score) will be compared using unpaired t tests. For the primary endpoint, analyses will be performed according to the intention-to-treat principle. Change in mean medication adherence between the 2 study groups (usual care and intervention) will be compared by using a t test for independent groups. Patients who do not complete the randomized trial (because of death or withdrawal) will be analyzed by the imputation method of last observation carried forward, using the medication adherence level of the time available. A similar methodology will be used for the secondary (exploratory) endpoints of diabetes control and re-admission rate.

Exploratory analysis: To control for baseline differences between study groups, a multivariable analysis will be performed for the randomized trial primary end point. The dependent variable for this analysis will also be the change score (the change in medication adherence between pre-treatment and post-treatment). The independent variables will be those baseline characteristics that had between group comparisons with $P < .20$, in addition to the randomized trial group assignment, clinic site and the baseline (run-in phase) medication adherence. The criteria for statistical significance for the primary outcomes will be a two-sided $p < 0.05$. The above statistical methodology is based on the approach used by Lee et al., JAMA 2006.

Target Population

We will recruit adults with independence Blue Cross medical and pharmacy coverage, Type II DM, HbA1C ≥ 7.5 , and a current medication regimen that only includes oral therapy. If patients are eligible for participation an initial meeting will be arranged with a trained research coordinator to enroll them in the study. This meeting will occur either in the clinic or in the patient's home in the case the patient is unable to commute to the clinic. Eligible participants will be randomized to either treatment or control arms with a target allocation ratio of 1:1. With the estimated sample size (75 treatment, 75 control) we have 80% power to detect up to a 15% change in medication adherence. This assumes a dropout rate of 15% percent and a standard deviation of 30%.

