Inclusion Criteria

We have structured the criteria to include patients who are most likely to benefit from the intervention. This includes patients are nonadherent based on pharmacy benefit claims data and whose blood sugar is not well controlled (HbA1C ≥ 7.5). Key inclusion criteria are:

- Insurance and pharmacy coverage with Independence Blue Cross (IBC)
- 18 years or older
- Current diagnosis of Type II Diabetes Mellitus
- HbA1C ≥ 7.5 (standards defined by the American Diabetes Association) as recorded in the clinical chart at last determination
- Less than 80% medication adherence for hypoglycemic medications as determined by pharmacy benefit data in the 9 months prior to the study
- Able to communicate in English
- Willing to give informed consent

Exclusion Criteria

Participants whose medications are dispensed are excluded because the intervention focuses on the patient, not their care facility. Not agreeing to use TowerView's connected pillbox is an exclusion because it is central to our intervention. Finally, not having access to a phone is an exclusion criteria because it is the only way our group can contact the patient if needed.

- Known alcohol or illicit drug abuse
- Significant cognitive impairment at baseline as defined by a Montreal Cognitive Assessment (MoCA) exam
- Residence in a care facility that provides medication on schedule
- Unwilling to use TowerView Health's connected pillbox and accompanying medication trays
- Any active medical or psychiatric diagnosis that, based on the clinical assessment of the research team, would prevent the study participant from completing the trial such as: markedly shortened life expectancy (e.g. diagnosis of metastatic cancer, end stage renal disease on dialysis, New York Heart Association (NYHA) Class III or IV heart failure, active psychosis or suicidal ideation, etc.) or dexterity/motor impairments (e.g. severe arthritis, neuromuscular disorders, etc)
- Lack a mobile or landline phone

Subject Recruitment and Screening

We will recruit 150 patients identified through the Pennsylvania Integrated Clinical and Administrative Research Database system and Independence Blue Cross/Catamaran databases. Patients with Type II DM, an HbA1C \geq 7.5, and IBC medical and pharmacy coverage will be identified.

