For patients taking multiple hypoglycemic agents the PDC for each drug is calculated then averaged to arrive at a mean group PDC. Mean group PDC will be used as a patient inclusion criteria as well as in the post study analysis for patients taking multiple hypoglycemic agents. Pre-study adherence rates will be determined using a 9-month estimate of PDC for the hypoglycemic drugs in a patient's medication schedule.

Measuring Persistence

Medication persistence relates to the length of time a patient remains on a medication without discontinuation. Patients are deemed to have discontinued therapy when more than 30 days have elapsed without a prescription refill. The persistence length will be calculated from the study start date to the expected end date of the last prescription prior to the patient discontinuing therapy.

Post Study Analysis

The primary outcome of interest in the present study is improvement in adherence; however, our group also plans to analyze the following secondary variables if the sample size allows:

- Medication Persistence
- Blood glucose (A1C)
- Blood pressure control
- Body mass index,
- ER visits
- Absolute costs,
- Overall healthcare utilization,
- Patient satisfaction with service,
- Time to first research coordinator outreach
- Number of research coordinator outreach events
- Text message and phone call trends

We also plan to perform regressions that explore how the following factors influence study outcomes:

- Age and Gender
- Insurance Line of Business (e.g. HMO, PPO, POS, MA HMO, MA PPO, etc)
- Pre-study medication adherence
- Pharmacy preference
- Type and number of comorbidities
- Patient drop-out from the study

Risks

Patients in the treatment group face potential confusion over use of new of device and mode of receiving their medication. This risk will be mitigated through patient education. Each patient will be trained on how to use the device as well as sent home with a detailed document highlighting how to use their smart pillbox and how to navigate the TowerView Health platform. Patients will also be given a number they can call at anytime to receive detailed assistance if challenges arise.

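### The primary test is an unadjusted t test on the PDC change score, although a baseline-adjusted model could be made primary with data already collected

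*Combined protocol and SAP*

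**What the plan says.** Statistical Analysis defines the primary variable as the post- minus pre-intervention PDC and says that its mean change in the two groups "will be compared by using a t test for independent groups". The test level is set thus: "The criteria for statistical significance for the primary outcomes will be a two-sided $p < 0.05".

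The same section plans a multivariable model of the same change score and labels it exploratory. Some terms are always included: "in addition to the randomized trial group assignment, clinic site and the baseline (run-in phase) medication adherence". The rest are screened on the data at a threshold of .20: "The independent variables will be those baseline characteristics that had between group comparisons with" (the sentence then gives that threshold).

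The baseline is available for every patient. Inclusion Criteria requires "Less than 80% medication adherence for hypoglycemic medications as determined by pharmacy benefit data in the 9 months prior to the study", and Measuring Adherence adds: "Pre-study adherence rates will be determined using a 9-month estimate of PDC for the hypoglycemic drugs".

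On sample size, Target Population says that with 75 per arm "we have 80% power to detect up to a 15% change in medication adherence". It continues: "This assumes a dropout rate of 15% percent and a standard deviation of 30" per cent. It does not say whether that SD belongs to the change score or to PDC at follow-up.

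**The concern.** Subtracting the baseline assumes that each point of baseline PDC carries forward as one point at follow-up. Patients are enrolled because their 9-month PDC was low, so regression to the mean, and hence a slope below 1, is plausible. Where the slope is not 1, the change score over- or under-corrects a chance baseline imbalance and carries avoidable variance. Study Design describes random number generation without stratification, so nothing in the design limits such imbalance.

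The plan already contains the adjusted model, but not in a form that could serve as primary:

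- **Covariate selection.** After randomisation, a between-group P<.20 picks out chance imbalance, not prognostic value. It makes the model depend on the data. The plan does not say which characteristics are screened; the measures under Induction Visit and the factors under Post Study Analysis are not tied to the rule.
- **Baseline definition.** The model's baseline is called run-in adherence, but no run-in phase is described anywhere else.

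At stake are the precision of the primary result and the ability to fix the adjusted model before data are seen. The type I error of the t test is not in question.

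**Working it through.** **1. The plan's own figure.** Inputs from Target Population and Statistical Analysis: difference 15 points (read as absolute), SD 30, two-sided 0.05, 80% power, 15% dropout, 75 per arm.

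- n per arm = 2 × (1.96 + 0.84)² × 30²/15² = 62.8, so 63. Then 63/0.85 = 74.1, so 75. This matches.
- Evaluable per arm = 75 × 0.85 = 63.75. Noncentral-t power is 80.0%.

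The sample size therefore stands if 30 is the SD of the change score.

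**2. Variance comparison.** Let s0 and s1 be the baseline and follow-up SDs, rho their correlation, and k = s0/s1.

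- Change score: s1²(1 + k² − 2·rho·k)
- Baseline-adjusted (ANCOVA): s1²(1 − rho²)
- Difference: (s0 − rho·s1)², which is never negative and is zero only when rho = s0/s1.

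This is a large-sample result. At the planned 1:1 allocation it survives different slopes in the two arms: a worked example gave an adjusted/unadjusted variance ratio of 0.83. In that example the ratio passed 1 only at about 30:70 allocation.

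**3. Power if 30 is the change SD.** The residual SD is 30 × √[(1 − rho²)/(1 + k² − 2·rho·k)]. For k = 0.69 and rho = 0.3 the variance ratio is 0.91/1.062 = 0.857, the residual SD is 27.8 and power is 85.7%. All k and rho are assumptions. The t test stays at 80.0% throughout. ANCOVA power (%), 63.75 per arm:

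| k | rho 0.3 | rho 0.4 | rho 0.5 | rho 0.6 |
|---|---|---|---|---|
| 0.6 | 83.6 | 81.8 | 80.5 | 80.0 |
| 0.69 | 85.7 | 83.6 | 81.8 | 80.5 |
| 0.8 | 88.5 | 86.4 | 84.2 | 82.3 |
| 1.0 | 93.5 | 91.7 | 89.9 | 87.9 |

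The k = 0.69 row takes the usual-care figure of 63% (26%) in the Hypothesis table (single-dose blister packaging, hypertension), treats it as normal and limits it to 0–80. That gives a baseline SD of 17.9, and 17.9/26 = 0.69. Equal SDs (k = 1) are the favourable case, because the eligibility cut narrows the baseline.

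**4. Power if 30 is instead the follow-up SD.** Over k 0.6–0.8 and rho 0.3–0.6, t-test power runs from 73.9% to 93.8% and ANCOVA from 83.6% to 93.8%. At rho 0.3 the t test has 80.0%, 77.6% and 73.9% for k = 0.6, 0.69 and 0.8, against 83.6% for ANCOVA in each case.

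**5. Simulation checks.**

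- Bivariate normal, 64 per arm, change SD 30, 20,000 runs, t test against ANCOVA: 0.801 v 0.853 (k 0.69, rho 0.3); 0.801 v 0.885 (k 0.8, rho 0.3); 0.803 v 0.799 (k 0.6, rho 0.6, where no gain is expected).
- Bounded PDC, baseline below 80%, site in the model: variance ratio 0.85 to 0.95 in three scenarios and 1.01 where the slope was close to 1. Type I error was 5.0–5.4% for ANCOVA and 4.9–5.5% for the t test.

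**6. The P<.20 rule.** With m independent, truly balanced characteristics, 0.2m are selected on average, and the chance of at least one is 1 − 0.8^m: 67% for m = 5, 89% for m = 10, 96% for m = 15. The values of m are assumed.

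**The case against.** The strongest reply is that nothing here is an error. The t test is unbiased under randomisation, the power reproduces, and the adjusted estimate is already planned; only its label would change. The P<.20 rule cannot touch the primary p value. All of this is true, and it makes the point an improvement in efficiency and pre-specification, not a correction.

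The gain may also be small or nil. The k = 0.69 row combines a ratio derived from an SD of 26 with a change SD of 30. If 26 and 17.9 are used on their own scale, t test against ANCOVA power is 88.1% v 92.3% at rho 0.3, 92.0% v 94.1% at 0.4, 95.4% v 96.2% at 0.5 and 98.0% v 98.1% at 0.6. The gain is then 0.1 to 4.3 points, with the t test above 80% throughout. That stands, and the size must be read as a range. The direction does not change.

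The powers above use 63.75 per arm, while the plan keeps non-completers by last observation carried forward. With 75 analysed per arm and an undiluted 15-point difference, t-test power is 86.0%, and ANCOVA at k = 0.69 gives 86.5% to 90.8%. Again the comparison moves but does not reverse.

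Finally, the run-in reference is probably a slip, and a change SD is the natural reading of the 30%. Neither gap would carry the point alone, but both must be closed to pre-specify the model. Clinic site needs a definition too: Length and Objectives names two hospitals and four clinic settings.

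**Conclusion.** The concern holds as a free improvement. The primary analysis is valid and adequately powered on the plan's inputs if 30% is the change SD. However, it ranks an unadjusted test above an adjusted one that uses data already in hand. At 1:1 allocation the adjusted model cannot lose large-sample precision. Its finite-sample cost is about 1% in variance if the covariates explain nothing, and at most 0.03 power points in degrees of freedom for up to five covariates.

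The gain cannot be fixed from the documents. Under the assumed k of 0.6–0.8 and rho of 0.3–0.6 it is 0 to 8.5 power points (80.0% to between 80.0% and 88.5%) when 30 is the change SD. If 30 is the follow-up SD, the t test could fall as low as 73.9% in that range, while ANCOVA stays at or above 83.6%. The specification gaps do not depend on these assumptions.

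**What to change.** In Statistical Analysis:

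1. Make the primary analysis a linear model of post-randomisation PDC on arm, 9-month pre-study PDC and clinic site, two-sided 0.05. With baseline in the model the arm estimate is the same for follow-up PDC as for the change score. This also settles the difference between the Study Summary, which names change in PDC as the primary endpoint, and the endpoint list, which names PDC rates.
2. Define clinic site (hospital or clinic type).
3. Keep the change-score t test as a supportive analysis.
4. Delete the P<.20 rule. Name any further covariates in advance.
5. Replace the run-in reference with the 9-month pre-study PDC defined under Measuring Adherence.

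In Target Population, state whether the 30% SD refers to the change score or to PDC at follow-up.

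The cost is wording only. No extra patients, visits or data are needed, and the sample size of 150 is unchanged.

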This randomized control trial will be carried out in an outpatient geriatric, endocrinology, internal medicine, and family medicine setting at both the Hospital of the University of Pennsylvania (HUP) and Presbyterian Hospital. Patients will be enrolled in the research study for 6 months. The overall study will end when the last patient has completed their 6-month observation period. Independence Blue Cross's informatics department will complete the post study analysis within 2 months of the study completion.

The primary aim of the study is: To determine if a multi-modal intervention focused on improving medication adherence among adults who were previously nonadherent to their oral hypoglycemic agents results in improved medication adherence over a 6-month interval

Secondary (exploratory aims) for the study are: To determine if the multi-modal intervention results in improved blood glucose, blood pressure, reduction in emergency room visits, reduction in absolute healthcare costs, and reduction in overall healthcare utilization

Post study analyses will explore how various demographic factors as well as accompanying comorbidities affect medication adherence in the treatment vs. control groups. Satisfaction with the multi-modal intervention will also be assessed through a survey instrument at the end of the 6-month study period.

Study Intervention

Patients in the research treatment group receive pre-filled, 3x7 disposable trays that separate their medication by dose and time (e.g. morning, afternoon, evening). These pre-filled trays are inserted into a connected, weekly pillbox that detects when pills are removed from its wells. Using this information, TowerView Health's system is able to send automated text messages or phone reminders to patients to take forgotten or ignored medication doses.

Medication adherence data from deployed pillboxes populates a software platform, which a research coordinator can access. Patients who miss *3 consecutive doses or 5 doses out of 12 over a 4-day period* trigger an alert for the study research coordinator who can contact the patient via phone call. The research coordinator follows a scripted motivational interview in his or her outreach to determine the etiology of non-adherence. Patients reporting worrisome symptoms will be instructed to contact their provider directly and/or go to the emergency room for immediate attention.

Our team acknowledges that the current study actually involves multiple interventions:

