We propose a randomized control clinical trial. Random number generation will be used to randomize patients to either the treatment group (connected pillbox) or control group (usual care). The patient will only be randomized after he or she has been briefed on the intervention and consented to participating. In this way both patients in the treatment and control groups will receive the same education regarding adherence so as to not bias the study. Patients in both the research treatment and control group will be compensated equally for their participation in the study.

Study Intervention

The study intervention is multi-modal and consists of 1) prefilled medication trays that are shipped to patient's home 2) a connected pillbox that senses when doses are missed and can initiate phone call or text reminders and 3) research coordinator outreach triggered by nonadherence. A detailed overview of each component of the intervention is presented below:

Prefilled Medication Trays

The study sponsor, TowerView Health, has developed plastic trays designed to hold all the medications in a patient's regime. Each tray has 21 medication compartments- 3 compartments (morning, afternoon, nightly meds) for each day of the week. Patients in the research intervention will receive monthly shipments of 5 prefilled medication trays from Friendship Pharmacy, Inc., an IBC participating long-term care and retail pharmacy, located at [name].

After consenting to participate in the study, the patient or patient's caregiver will provide the research coordinator with a complete list of pharmacies used by the patient. This information will be shared with the Friendship Pharmacy pharmacist who will initiate the transfer of all scripts from patient's existing pharmacy to Friendship Pharmacy. A nurse practitioner or physician at Penn Medicine will initiate any scripts that need to be rewritten. In instances where prior authorization is required or a script is denied at adjudication the Friendship pharmacist will reach out to the physician or nurse practitioner to receive authorization or make an appropriate medication change.

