Patients will be consented by a trained research coordinator and have the following information collected from them:

- Electronic mailing address and phone number
- Blood pressure-once at the beginning and once at the end of the visit
- Demographic survey
- Montreal Cognitive Assessment (MoCA exam)- a screen for cognitive impairment
- Cumulative Illness Rating Scale (CIRS)- a measure of comorbid illness burden
- Short Form 12 (SF-12)- a measure of general quality of life
- Brief Medication Question (BMQ)- a self reported assessment of medication adherence and medication adherence related factors (e.g. cost burden of drugs)

Concluding Visit

Patients will return their connected pillbox and have the following information collected from them:

- Blood pressure- once at the beginning and once at the end of the visit
- HbA1c test and lipid panel if data cannot be abstracted from the chart
- Patient satisfaction and attitudes toward adherence system

The care coordinator will also assist the patient in transitioning from the tray to another method of receiving their medications. Patients will have the option of either remaining with Friendship Pharmacy or be transferred back to their original pharmacy.

Methods

Measuring Adherence

Proportion of Days Covered (PDC) is the metric currently used by CMS and NCQA to assess patient medication adherence; the metric is calculated using pharmacy benefit data. The present study utilizes an interval-based PDC calculation defined as medication possession during the interval from the index date (the patient's study start date) to the end of the period being assessed (the patient's end date). In this way, the number of days of medication supplied throughout the period becomes the numerator and is divided by the number of days in the overall period itself. Intervals during which patients are hospitalized or in hospice are excluded from the PDC calculation

As PDC is an assessment of medication adherence for a single drug the calculation must be modified for patients taking multiple medications. Of interest in this study is patient adherence to oral hypoglycemic drugs. Our group recognizes the following categories as oral hypoglycemic agents: sulfonylurea, metformin hydrochloride, glitazones, acarbose, and meglitinides.

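### Last observation carried forward gives patients who withdraw a short-window PDC when six-month claims PDC can normally be obtained, contrary to the stated intention-to-treat analysis

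*Combined protocol and SAP*

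**What the plan says.** Under Statistical Analysis, the primary endpoint is the change in PDC, compared between arms by an unpaired t test, and "analyses will be performed according to the intention-to-treat principle". Patients who die or withdraw "will be analyzed by the imputation method of last observation carried forward, using the medication adherence level of the time available".

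Other sections bear on that rule:

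- **Source of the outcome.** Measuring Adherence says of PDC that "the metric is calculated using pharmacy benefit data". Length and Objectives assigns the post-study analysis to the insurer's informatics department. Inclusion Criteria require the insurer's coverage at entry.
- **Window.** Length and Objectives asks whether the intervention "results in improved medication adherence over a 6-month interval". Measuring Adherence runs PDC from study start "to the end of the period being assessed", which it equates with the patient's end date. That date is not defined for someone who leaves early.
- **Baseline.** "Pre-study adherence rates will be determined using a 9-month estimate of PDC" for the hypoglycemic drugs.
- **First fill.** In the treatment arm the study pharmacist must "initiate the transfer of all scripts" to the study pharmacy before trays are supplied (Prefilled Medication Trays). Controls keep their pharmacy (Post Enrollment Events).
- **Ways of leaving.** Early Withdrawal of Subjects allows removal for not following instructions. Compensation allows disenrolment when the cost difference at the study pharmacy is too large to cover.

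**The concern.** Last observation carried forward was devised for outcomes that stop being observed when a patient leaves. Claims-based PDC needs no visit, device or contact, and leaving the study does not by itself end coverage. On its natural reading, the rule sets aside data that can normally be had.

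Three consequences follow. First, for leavers the primary analysis does not measure six-month adherence as randomized. Second, their change score subtracts a nine-month baseline from a window that may last only weeks, in which one fill can dominate the ratio. Third, the error need not cancel between arms: the first tray waits on a script transfer, and disenrolment over pharmacy-transfer cost can occur only in the treatment arm. The result then depends partly on when and why patients leave.

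**Working it through.** **1. The plan's own figure.** Inputs from Target Population and Statistical Analysis: difference 15 (read as percentage points), SD 30, two-sided alpha 0.05, power 80%, dropout 15%.

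n per arm = 2 × (1.960 + 0.842)² × (30/15)² = 62.8, so 63. After dropout, 63/0.85 = 74.1, so 75. This reproduces the plan; the concern does not rest on a sample-size error. The assumed dropout is 0.15 × 75 = 11.25 patients per arm.

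**2. Extreme single patient.** One 30-day fill on day 0, exit at day 30, no later fill: truncated PDC is 30/30 = 100%, and six-month PDC is 30/182 = 16.5%.

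**3. Fill timing alone, with identical behaviour.** Assumptions, none from the documents except the 15%: 30-day fills; exponential gaps averaging 20 days (long-run PDC 30/50 = 60%); controls start at a random point in the refill cycle; treatment patients fill nothing before the first tray; PDC counts covered days up to exit day W or to day 182; all leavers exit on the same day. There were 30,000 simulated patients per scenario.

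Shift in the arm difference = 0.15 × [(T_W − T_182) − (C_W − C_182)], where T and C are the mean PDCs of treatment and control leavers.

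First tray on day 0, supply in hand at start not credited:

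| W | T_W | C_W | Shift |
|---|---|---|---|
| 30 | 100 | 31.2 | +8.9 |
| 60 | 74.7 | 45.8 | +2.9 |
| 90 | 69.4 | 50.5 | +1.4 |
| 120 | 67.2 | 52.9 | +0.7 |

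Day-182 values are 64.8 (treatment) and 55.3 (control). At day 30: 0.15 × [(100 − 64.8) − (31.2 − 55.3)] = 0.15 × 59.3 = 8.9. A hand check on controls: average supply in hand is 0.6 × 15 = 9 days, so covered days are about 0.6W − 9, giving 9/30 = 30% at day 30 and 100.2/182 = 55.1% at day 182. This agrees apart from whole-day counting.

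Other first-tray dates and supply rules, shift in points:

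| Scenario | Day 30 | Day 60 | Day 90 | Day 120 |
|---|---|---|---|---|
| Tray day 14, not credited | +2.6 | +1.2 | +0.8 | +0.4 |
| Tray day 20, not credited | -0.1 | +0.8 | +0.5 | +0.2 |
| Tray day 0, credited in both arms | +5.3 | +1.5 | +0.7 | +0.3 |
| Tray day 20, credited in both arms | -0.4 | +0.7 | +0.5 | +0.2 |
| Tray day 20, credited in controls only | -3.7 | -0.6 | -0.2 | -0.1 |

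Repeat runs agree to about 0.2 points.

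**4. Behaviour change after leaving.** Assume 15% of the treatment arm leaves and control leavers carry no such error. If treatment leavers gain 15 points while enrolled and then return to baseline, the overstatement is 0.15 × 15 × (1 − W/182) = 1.9, 1.5, 1.1 and 0.8 points for exits at day 30, 60, 90 and 120. If they run 30 points below baseline before removal and then return to it, the understatement is 0.15 × 30 × (1 − W/182) = 3.8, 3.0, 2.3 and 1.5 points.

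**5. Effect on the test.** With 75 per arm and SD 30, SE = 30 × √(2/75) = 4.90. If the true six-month difference is zero, the noncentral t distribution gives two-sided rejection rates of 5.5% for a 1-point bias and 9.3% for a 3-point bias.

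**The case against.** The strongest counter-case has five parts.

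- **Everyone is still analysed.** The rule keeps all 150 patients in their assigned arms, so intention-to-treat is not breached as to who is counted. This is correct. The conflict is with following the outcome over the planned period whatever happens to treatment.
- **Claims access after withdrawal is inferred.** No section says claims may be used once a patient leaves, coverage is established only at entry, and the consent pages are not in the reviewed copy. This stands as a limit, and the fix allows for it.
- **Truncation is a reading.** The time available could mean all available claims. The carried-forward wording and the undefined end date point the other way. If full claims were intended, the plan still has to say so.
- **The large shifts are corner cases.** They need every leaver to go at day 30, and the documents give no distribution of exit times. Counting supply in hand for controls only has no support in the text. The simulation counts covered days, whereas Measuring Adherence describes days supplied over days in the period. On that literal numerator, a 30-day fill on day 20 of a 30-day window scores 30/30 = 100% rather than 10/30 = 33%. So the figures illustrate sensitivity and do not predict a bias.
- **Cost disenrolment may be rare.** Compensation plans cost parity, sponsor top-up and the option to stay at higher cost. This is fair: the route exists only in the treatment arm, but its frequency is unknown.

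First-fill timing also affects completers: under the same assumptions the day-182 values differ between arms by -1.8 to +9.5 points. The proposed change does not address that.

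**Conclusion.** The concern holds and should be fixed. The stated rule substitutes a truncated PDC for a six-month claims value that is normally obtainable, and leaves the end of the window undefined for the patients to whom it matters.

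The direction of bias is not fixed. An early first tray, or a gain that fades after leaving, favours treatment; a late first tray, or poor adherence before removal, can reverse it. With 15% leaving each arm and supply counted alike, the fill-timing shift ranges from negligible to about 9 points for day-30 exits, falls to at most 2.9 by day 60, and is about 1 point or less for later exits. The behaviour-change scenarios give 0.8 to 3.8 points in either direction. All of this is conditional on assumed refill patterns, exit days and post-exit adherence; only the dropout rate, SD and target difference are the plan's. Availability of claims after withdrawal is an inference from the claims source, coverage at entry and the insurer's role.

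**What to change.** In Statistical Analysis and Measuring Adherence:

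1. For the primary endpoint, compute PDC from insurer claims from study start to the planned six-month date for every randomized patient, regardless of withdrawal, removal or return of the device. Define the end date to match.
2. End the window early only at death, loss of the insurer's coverage or withdrawn permission to use claims. Report the number, reason and day of each by arm.
3. Keep last observation carried forward at most as a sensitivity analysis, alongside one that assumes return to baseline PDC after exit.
4. Check that the consent covers claims follow-up after a patient leaves the intervention.

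The cost is wording in two places and a consent check; the claims source is already in use. No power gain is claimed, because the current rule already analyses all 150. The estimate may be less favourable. If 15% of the treatment arm leaves at month 1 with a 15-point gain that then disappears, the six-month effect is 0.85 × 15 + 0.15 × 15 × 1/6 = 13.1 points, and power at 75 per arm is 0.764, against 0.865 for a 15-point effect. Deaths, lost coverage and refused access will still lack a full window.
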